10. TREATMENT OF PARTICIPANTS

10.1. Description of Study Drug

Table 18: Investigational Product

	Investigational Product			
Product Names: *	AXO-AAV-GM2			
Active Ingredients:	AAVrh8- HEXA	AAVrh8- HEXB		
Dosage Form:	Solution (0.5mL vials)	Solution (0.5mL vials)		
Concentration: **	4.32E+13 vg/mL	2.62E+13 vg/mL		
Combined Vector:	Each vector is diluted together without the addition of any diluent to yield a final titer of 1.63E+13 vg/mL for each, HEXA and for HEXB , and a combined titer of 3.26E+13 vg/mL			
Formulation:	1.47mM KH ₂ PO ₄ , 8.06mM Na ₂ HPO ₄ -7H ₂ O, pH 7.1 ± 0.1, 137.93mM NaCl, 2.67mM KCl	1.47mM KH ₂ PO ₄ , 8.06mM Na ₂ HPO ₄ -7H ₂ O, pH 7.1 ± 0.1, 137.93mM NaCl, 2.67mM KCl		
Route of Administration:	BiTh and ICM/IT	BiTh and ICM/IT		
Physical Description:	The biologic product is a non-replicating, serotype rh8, single-stranded (ss) recombinant adeno-associated virus (rAAV) designated rAAVrh8-HEXA	The biologic product is a non-replicating, serotype rh8, single-stranded (ss) recombinant adeno-associated virus (rAAV) designated rAAVrh8-HEXB		

^{*} Study drug consists of two components, labeled and supplied in two separate vials as AAVrh8-CB-ci-HEXA and AAVrh8-CB-ci-HEXB as described in Section 11.1. AXO-AAV-GM2 refers to the combination of these two components into a single dose.

10.2. Concomitant Medications

All prescription and over the counter medications (including herbal remedies) taken by the participant for 28 days prior to administration of immunosuppressive regimen will be recorded on the source document and eCRF. Concomitant medications taken by the participants during the LTFU period will also be recorded on the source documents/eCRF. The Investigator may prescribe additional medications during the study, as long as the prescribed medication is not prohibited by the protocol. In the event of an emergency, any required medications may be prescribed without prior approval, but the Medical Monitor or designee must be notified of the use of any contraindicated medications immediately thereafter. Any concomitant medications added or discontinued during the study will be recorded on the eCRF, including the start and end dates, as applicable.

Concurrent supportive care for TSD or SD will not be restricted with exception of exclusionary medications. Therapies considered necessary for the participant's well-being will be administered at the discretion of the investigator.

Confidential Page 72 of 97

^{**} Concentration is based on ddPCR titers measured for lots produced at Nationwide Children's Hospital (June 2019) that will be used for Stage 1 of the clinical trial.

Clinical Study Protocol: AXO-GM2-001

Version 8.0, 09 June 2023

10.3. Treatment Compliance

Since AXO-AAV-GM2 is a one-time surgical administration, treatment compliance to gene therapy will not be assessed.

10.4. Randomization and Blinding

Stages 1 and 2 of the study have a single-arm, open label design. Randomization or blinding will not be performed.

Confidential Page 73 of 97

Version 8.0, 09 June 2023

11. STUDY DRUG MATERIALS AND MANAGEMENT

11.1. Study Drug

AXO-AAV-GM2 is a 1:1 formulation of two viral vectors, rAAVrh8-HEXA and rAAVrh8-HEXB, carrying different human transgenes. One of the vectors contains the human HEXA gene, encoding for the HexA α subunit, and the other contains the human HEXB gene, encoding for the HexA β subunit. Both vectors utilize a CBA promoter, a chimeric intron, BGH/SV40 polyA tail, and AAV serotype 2 inverted terminal repeats (ITR).

11.2. Study Drug Packaging and Labeling

Study drug will be supplied in polypropylene screw top 0.5 mL tubes (vials). Each vial will be filled with 0.5 mL of rAAVrh8-*HEXA* or rAAVrh8-*HEXB*. The vials are packed and stored in plastic cryoboxes. Both the vials and cryoboxes will be labeled in accordance with the requirements set by the FDA. The vial labels will each contain a unique identifier for ease of tracking.

11.3. Study Drug Storage

All study drug vials are to be stored in freezers at less than or equal to -60° C. The freezers must be monitored daily and any deviation in temperature $> -60^{\circ}$ C must be reported to the sponsor as soon as possible and prior to further clinical use of the study drug. The study drug must be stored in such a way that it cannot be mixed up or confused with any other medications.

11.4. Study Drug Preparation

All prescriptions for study drug are to be written by the site Principal Investigator . A separate prescription is needed for the BiTh and the ICM/IT procedures. The prescriptions for these procedures must be accompanied by the Dose Preparation Forms.

Preparation of both the BiTh and ICM/IT doses must be done in accordance with the Pharmacy Manual for the study, and all institutional SOPs and practices required for the handling of biologic and/or potentially hazardous materials. Preparation of the study drug must be performed by the Research Pharmacist or trained designee, who must be listed on the Site Delegation Log and be trained on the Pharmacy Manual. Because each full dose of study drug is comprised of two components (AAVrh8-HEXA and AAVrh8-HEXB), a second qualified and trained member of the study team must be present during the study drug preparation process and must verify quantity of each drug component used, and that all processes were followed. This person must also be listed on the Site Delegation Log and be trained the Pharmacy Manual.

11.5. AXO-AAV-GM2 Administration

The Surgical Manual will contain detailed specific instructions for administration of AXO-AAV-GM2 which will take place over two days beginning with BiTh procedure at Visit 1a and ICM/IT procedure at Visit 1b (See Table 14 and Table 15).

Confidential Page 74 of 97

Clinical Study Protocol: AXO-GM2-001

Version 8.0, 09 June 2023

11.5.1. Stage 2 Dosing

The dose strategy for Stage 2 will be determined by Stage 1 safety and biomarker results.

11.6. Study Drug Accountability

Study drug accountability will be performed routinely by the Sponsor or Sponsor's representative. The site must maintain accurate and current records of all drug received, all drug used during the procedures (including back up drug), all drug remaining on site, and all drug destroyed if applicable.

11.7. Study Drug Handling and Disposal

Storage and dispensing of the study medication will be conducted in accordance with the Pharmacy Manual and the overview below.

AXO-AAV-GM2 is a frozen liquid formulation. Study drug must be inspected and inventoried upon receipt, and placed into appropriate storage conditions (≤-60°C), in a monitored, temperature-controlled freezer located within the hospital pharmacy, in accordance with site SOPs and procedures for GMO handling.

AXO-AAV-GM2 may only be used for the clinical trial for which it is indicated and must not be employed for any other clinical or non-clinical use.

Confidential Page 75 of 97

UMass Chan Medical School Clinical Study Protocol: AXO-GM2-001 Version 8.0, 09 June 2023

12. ASSESSMENT OF EFFICACY

Assessment of efficacy within this study will include:

- CSF HexA activity and GM2 ganglioside level
- Serum HexA activity
- BSID-III
- HINE-2
- MRI
- DTI
- MRS
- BAER
- VER
- Clinical Global Impression
- Vineland-3
- Wechsler scale (Wechsler 5, WPPSI, etc)
- GMFM-88
- GMFC-MLD
- 9-Hole Peg Test
- The Pediatric Balance Scale
- Timed Motor Function Tests (10 Meter Walk/Run, Time to Rise from Floor, Time Up 4 Stairs)
- SSEP

Please see the Study Schedule of Events (Table 14 and Table 15) for the timing of these assessments.

Several assessments included in this study will be administered by raters trained in the administration of the assessment. To minimize variability, it is preferred that the same rater administer the same scale to the same participant throughout the study wherever possible, at the same time during the clinic visit.

Confidential Page 76 of 97

UMass Chan Medical School Clinical Study Protocol: AXO-GM2-001 Version 8.0, 09 June 2023

13. SAFETY PARAMETERS

13.1. Vital Signs, Height, and Weight

Vital signs will be measured after the participant has been at rest. Measurements will include systolic and diastolic blood pressure, pulse rate per minute, respiratory rate per minute, and temperature. Height will be measured in centimeters as the length of the participant in the supine position. Weight will be recorded in kilograms.

A vital sign result should be reported as an AE if it meets any of the following criteria:

- Accompanied by clinical symptoms
- Results in a medical intervention or a change in concomitant therapy
- Clinically significant in the investigator's judgement

13.2. Physical Examination

Physical and neurological examinations will be performed per the Schedule of Events. The assessments included in the exams will be at the discretion of the clinician based on the status of the participant at the time of the assessment.

13.3. Electrocardiogram (ECG), Electroencephalogram (EEG)

A standard 12-lead ECG will be performed per the Schedule of Events and reviewed by a cardiologist. A copy of the tracings will be kept on site as part of the source documents.

A standard EEG will be performed and reviewed by a neurologist. Whether a 1hr or 24hr EEG is performed will be at the discretion of the neurologist.

13.4. Laboratory Assessments

Laboratory assessments for safety will be performed by the site's local laboratory, and all certification/qualification documentation will be on file in the TMF. A laboratory test result should be assessed as clinically significant or not clinically significant, and should be reported as an AE if it meets any of the following criteria:

- Accompanied by clinical symptoms
- Results in a medical intervention or a change in concomitant therapy
- Clinically significant in the investigator's judgement

If a clinically significant laboratory abnormality is a sign of a disease or syndrome (e.g., hemoglobin below the lower limit of normal associated with anemia), only the diagnosis should be recorded. If the abnormality is not a sign of a disease or syndrome, the abnormality itself should be recorded (e.g., low calcium).

13.4.1. Hematology

Hematology panel: complete blood count with auto-differential (hematocrit, hemoglobin, platelet count, RBC indices, total RBC, total WBC, and WBC differential)

Confidential Page 77 of 97

Version 8.0, 09 June 2023

13.4.2. Blood Chemistry

Blood chemistry: comprehensive metabolic panel, including albumin, albumin/globulin ratio (calculated), alkaline phosphatase, ALT, AST, BUN/Creatinine Ratio (calculated), Calcium, Carbon Dioxide, Chloride, Creatinine with GFR Estimated, Globulin (calculated), Glucose, Potassium, Sodium, Total Bilirubin, Total Protein, Blood Urea Nitrogen (BUN)

13.4.3. Urinalysis

Urinalysis by dipstick bag: bilirubin, blood, clarity, color, glucose, ketones, nitrite, pH, protein, specific gravity, urobilinogen and leukocyte esterase

13.4.4. Virus Serology

Infectious disease testing: hepatitis B, herpes simplex virus, cytomegalovirus, Epstein-Barr virus, varicella zoster virus, and toxoplasmosis.

13.4.5. CNS

- Anti-seizure drug levels
- Cerebral spinal fluid (CSF) assessments: color, appearance, WBC count, RBC count, glucose, protein

13.4.6. Immunology

- B-Cell count
- IgA levels, to determine if an IgA deficient immunoglobulin needs to be used during IVIG
- Quantitative serum IgG, for determining dosing of IVIG
- Blood collected for research can include anti-AAVrh8 antibodies (ADA), transgene antibodies (ADA) and neutralizing antibodies (Nabs) if needed.
- ELISpot for assessment of capsid and transgene antigen-specific interferon gamma producing T cells in human PBMCs

13.4.7. Vector Shedding

Viral shedding will be assessed in Stage 2; the matrices and time points will be added to the schedule of assessments via protocol amendment.

13.5. Chest X-Ray

Anteroposterior and lateral chest X-ray will be performed at the first visit (Day -16) and then only as clinically indicated.

13.6. Imaging: MRI, MRS, DTI

Magnetic resonance imaging (MRI), magnetic resonance spectroscopy (MRS). diffusion tensor imaging (DTI), and computerized tomography (CT) scans will be performed under general anesthesia (with or without intubation at discretion of investigator).

Confidential Page 78 of 97

Clinical Study Protocol: AXO-GM2-001

Version 8.0, 09 June 2023

13.7. Ophthalmology

Complete ophthalmologic examination will be performed and documented by an ophthalmologic specialist.

13.8. Brainstem Auditory Evoked Response (BAER)

Standard BAER testing for auditory acuity will be documented.

13.9. Adverse and Serious Adverse Events

13.9.1. Definition of Adverse Events

13.9.1.1. Adverse Event (AE)

According to the International Conference of Harmonization (ICH) guideline for Good Clinical Practice, an AE is any untoward medical occurrence in a patient administered pharmaceutical product and which does not necessarily have a causal relationship with this treatment.

An AE can therefore be any of the following:

- Unfavorable and unintended sign (including an abnormal laboratory finding), symptom, or disease temporally associated with the use of a medicinal (investigational) product, whether or not considered related to the medicinal (investigational) product.
- Any new disease or exacerbation of an existing disease (a worsening in the character, frequency, or severity of a known condition)
- Recurrence of an intermittent medical condition (e.g., headache) no present at baseline
- Any deterioration or abnormality in a laboratory value or other clinical test (e.g., ECG, X-ray) that is associated with symptoms or leads to a change in the study treatment or concomitant treatment or discontinuation from the study drug
- Adverse events that are related to a protocol-mandated intervention, including those that occur prior to assignment of study treatment.

All AEs will be captured following the signing of the informed consent form.

13.9.1.2. Serious Adverse Event (SAE)

A serious adverse event is an AE occurring during any study phase (i.e., baseline, treatment, washout, or follow-up), and at any dose of the investigational product, comparator or placebo, that fulfils one or more of the following:

- Results in death
- It is immediately life-threatening
- It requires in-patient hospitalization or prolongation of existing hospitalization
- It results in persistent or significant disability or incapacity
- Results in a congenital abnormality or birth defect

Confidential Page 79 of 97

Version 8.0, 09 June 2023

• It is a significant medical event in the investigator's judgement (e.g., may jeopardize the participant or may require medical/surgical intervention to prevent one of the outcomes listed above).

All SAEs that occur following signing of the informed consent form, regardless of treatment arm, must be reported within 24 hours of the investigator becoming aware of the event.

13.9.1.3. Adverse Events of Special Interest (AESI)

Dose-limiting toxicities (DLTs) in this study are defined as adverse events of special interest (AESIs). The following AESIs are included specifically for AAV vector gene therapy delivered directly to the CNS by convection enhanced delivery

- Infusion-related reactions (adverse event occurring within 24 hours of gene therapy infusion)
- Neurosurgical related complications
- Type I Hypersensitivity Reaction
- Liver function test elevations: (Hy's Law) ≥3x elevations above the ULN of ALT or AST, serum total bilirubin >2xULN
- Thrombocytopenia defined as a platelet count <150,000/μL
- Delayed adverse events including but not limited to autoimmune-like reactions
- Malignancies

13.10. Relationship to Investigational Product, Study Procedure and Administration System

An Investigator who is qualified in medicine must make the determination of relationship between an AE and the investigational product received, study procedure and/or administration system (e.g., not related, unlikely related, possibly related, probably related, or definitely related). The Investigator should decide whether, in his or her medical judgment, there is a reasonable possibility that the event may have been caused by the investigational product, study procedure and/or administration system.

If there is any valid reason, even if undetermined, for suspecting a possible cause-and-effect relationship between the investigational product and the occurrence of the AE, then the AE should be considered "related."

If the relationship between the AE/SAE and the investigational product is determined to be "possible" or "probable" the event will be considered to be related to the investigational product for the purposes of expedited regulatory reporting.

When assessing a potential relationship between the investigational product, study procedure and/or administration system and an AE, the following parameters should be considered:

- Temporal relationship between the investigational product, surgical procedure and/or protocol-specified procedures and the AE
- The biological plausibility that the investigational product, study procedure and/or administration system caused the event

Confidential Page 80 of 97

AXO-AAV-GM2

UMass Chan Medical School Clinical Study Protocol: AXO-GM2-001

Version 8.0, 09 June 2023

- Any underlying/concurrent illness in the participant
- Concomitant medications the participant may have received
- How commonly the event occurs in the study population independent of treatment

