	Participant (J)	4.70E+13 vg	1.71E+14 vg	2.18E+14 vg
Cohort 1	Participant (I)	4.70E+13 vg	1.71E+14 vg	2.18E+14 vg
(Mid-Dose)	Participant (I)	4.70E+13 vg	1.71E+14 vg	2.18E+14 vg
	Participant (I)	8.15E+13 vg	2.74E+14 vg	3.56E+14 vg
Cohort 2 (High-Dose)	Participant (I)	8.15E+13 vg	2.74E+14 vg	3.56E+14 vg

Note: Dosing based on final titer of 3.26E+13 vg/mL (1:1 mixture of AAVrh8-HEXA:AAVrh8-HEXB)

Stage 2 dosing regimen will be determined based on Stage 1 results.

Duration of treatment: AXO-AAV-GM2 will be administered as a single, two-part procedure

Reference Therapy, Dosage and Mode of Administration: N/A

Criteria for Evaluation:

Stage 1

Stage 1 Primary Endpoint:

• The incidence, severity, seriousness, and relatedness to treatment of treatment emergent adverse events (TEAEs) as graded NCI CTCAE v5.0

Stage 1 Secondary Endpoints:

- Safety and immunologic response endpoints
- Changes in vital signs including weight
- Changes in physical examination findings
- Changes in clinical safety laboratory tests
- Immunosuppression response markers

Stage 1 Exploratory Endpoints:

- Changes from baseline in developmental age-appropriate clinical function assessments
 - Infantile participants: Bayley Scales of Infant and Toddler Development, Third
 Edition (BSID-III), Hammersmith Infant Neurological Examination Section 2
 (HINE-2; motor), Clinical Global Impression (CGI), Vineland-3 Neurological exam

Confidential Page 13 of 97

Version 8.0, 09 June 2023

- Juvenile participants: Neurocognitive function (as measured by the Wechsler, WPSSI, BSID-III depending on the participant's developmental age), Vineland-3, CGI, Neurological exam, fine and gross motor function and classification (as measured by GMFM-88, GMFC-MLD, timed motor function tests, 9-hole peg test, and the Manual Ability Classification System (MACS))
- Biomarker changes from baseline in:
 - Serum HEXA activity level
 - CSF HEXA activity level
 - GM2 ganglioside in CSF
- Change from baseline in brainstem auditory evoked response (BAER) and visual evoked response (VER) from baseline to Week 12 and Week 48
- MRI brain volume and Diffusion Tensor Imaging (DTI) indices of myelination and brain water change from baseline to Week 12 and Week 48
- MRS indices of metabolite accumulation change from baseline to Week 12 and Week 48

Stage 1 Juvenile-Onset Participant Efficacy:

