8.2. Prophylactic Immune Tolerance Induction (ITI) Regimen

To prevent the risks of an inflammatory response and to protect AAV-transduced cells from immune response to the AAVrh8 capsid and/or transgene, participants will be immunosuppressed prior to administration of AXO-AAV-GM2 treatment. The ITI regimen will be maintained as described below.

Starting on Day -7 of the study, the following will be initiated:

- Rituximab* at 375 mg/m² BSA (IV infusion)
 - *Pre-medication for rituximab infusion will include:
 - acetaminophen 10-15 mg/kg given either PO, g-tube or rectal one time prior to infusion (may repeat q 4 hours for temperature >38.3°C)
 - diphenhydramine 1 mg/kg given either PO, g-tube or IV one time prior to infusion (may repeat 1 mg/kg IV PRN)
- Solu-Medrol at 10 mg/kg (IV infusion)
- Sirolimus* at 1.5 mg/m² BSA/day (PO or by feeding tube) *adjustment permitted to achieve trough levels of 7-12 ng/mL
- Prednisolone at 1-2 mg/kg/day (PO or by feeding tube)
- Lansoprazole at 1-1.5 mg/kg/day (PO or by feeding tube)
- Trimethoprim/sulfamethoxazole 2.5 mg/kg/day BID on 2 consecutive days per week (PO or by feeding tube) or per PI discretion

Day -2, Day 1 (BiTh Infusion Day), Day 2 (ICM/IT Infusion Day):

• Rituximab* at 375 mg/m² BSA (IV infusion), as needed for persistent CD20 count ≥ 5%

*Pre-medication for rituximab infusion will include:

- acetaminophen 10-15 mg/kg given either PO, g-tube or rectal one time prior to infusion (may repeat q 4 hours for temperature >38.3°C)
- diphenhydramine 1 mg/kg given either PO, g-tube or IV one time prior to infusion (may repeat 1 mg/kg IV PRN)
- Continuation of sirolimus*, prednisolone, and lansoprazole dosing (PO or by feeding tube)
 - *adjustment permitted to achieve trough levels of 7-12 ng/mL
- Continuation of trimethoprim/sulfamethoxazole 2.5 mg/kg/day BID on 2 consecutive days (PO or by feeding tube) or per PI discretion

Day 2-8:

- Continuation of sirolimus*, prednisolone, and lansoprazole dosing (PO or by feeding tube)
 - *adjustment permitted to achieve trough levels of 7-12 ng/mL
- Continuation of trimethoprim/sulfamethoxazole 2.5 mg/kg/day BID on 2 consecutive days per week (PO or by feeding tube) or per PI discretion

Confidential Page 40 of 97

Clinical Study Protocol: AXO-GM2-001

Version 8.0, 09 June 2023

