The ITI regimen will be stopped upon evidence of any of the following severe conditions for which no other cause has been identified: (1) intractable, severe opportunistic infections, not able to be managed with antibiotic, antifungal or antiviral therapy; (2) renal dysfunction (rising creatinine or BUN); (3) severe rash; (4) evidence of CNS problems including seizures or encephalopathy; (5) bleeding or clinically significant elevation of bleeding parameters.

Participants requiring discontinuation of the ITI regimen prior to Visit 1a (Day 1) will not be eligible for gene transfer and will be withdrawn from the study.

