- Pancreatic enzymes

Based on the following thresholds

- Platelet count ($< 150,000/\mu L$)
- Prothrombin (PT), partial thromboplastin time (PTT) >2X normal
- Liver transaminases (Hy's Law: > 3x elevations above the ULN of ALT or AST and serum total bilirubin > 2xULN)
- 16. Participants for whom any of the proposed study procedures or medications (i.e. sirolimus, trimethoprim/sulfamethoxazole) would be contraindicated
- 17. Failure to thrive, defined as falling 20 percentiles (20/100) in body weight in the 3 months preceding Screening/Baseline
- 18. Participant is not suitable for participation in the study in the opinion of the Principal Investigator

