14.3. Analysis Populations

There are two pre-defined analysis populations in this study.

- Safety Population: All participants treated with study treatment (either a partial dosing or a complete dosing) will be included in the Safety Population. All safety analyses (e.g., adverse events, clinical laboratory) will be performed using the Safety Population.
- Intent-to-Treat Population: The Intent-to-Treat (ITT) population will be defined as all Safety Population infantile-onset participants from Stage 2 who have received the full dose of study medication. All efficacy analyses will be performed using the ITT population. This is the primary population of interest for efficacy assessments.

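### The immunosuppression regimen has no causality category of its own, and children withdrawn for its toxicity before Day 1 fall outside every planned safety analysis

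*Combined protocol and SAP*

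**What the plan says.** Section 8.2 sets out rituximab, intravenous and oral corticosteroid, sirolimus and supportive drugs: "Starting on Day -7 of the study, the following will be initiated". It lists severe conditions that stop the regimen when no other cause is found, and adds: "Participants requiring discontinuation of the ITI regimen prior to Visit 1a (Day 1) will not be eligible for gene transfer". Such a child is withdrawn. Section 8.7 names the regimen as a source of known risk, alongside the vector and its delivery.

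Section 13.10 says that a medically qualified investigator "must make the determination of relationship between an AE and the investigational product received, study procedure and/or administration system". Among the factors to weigh are "Temporal relationship between the investigational product, surgical procedure and/or protocol-specified procedures and the AE" and "Concomitant medications the participant may have received". Section 14.6 plans AE incidence by relationship to study medication.

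Section 14.3 states: "All participants treated with study treatment (either a partial dosing or a complete dosing) will be included in the Safety Population". The same section assigns all safety analyses to that population. Section 10.1 defines study drug as the two vectors.

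The Stage 1 primary endpoint (Synopsis) is the incidence, severity, seriousness and treatment-relatedness of treatment-emergent AEs (TEAEs). No start point for treatment emergence is given. Section 8.1.1 allows an added participant after a related AE of Grade 3 or higher within four weeks, without saying what the event must be related to.

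**The concern.** All participants receive two interventions with serious potential harms: the vector with its neurosurgical delivery, and a multi-drug immunosuppression regimen. The plan records attribution for the first and not for the second. An infection or a rise in creatinine caused by the regimen has no place of its own on the causality scale, so no planned analysis can say how much of the observed harm came from the regimen.

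Separately, toxicity bad enough to stop the regimen before Day 1 removes the child from the population on which all safety analyses are run. Those are the most severe early regimen failures. A reader of the safety tables would not see them, although any later patient would face the same regimen before gene transfer.

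The two remaining ambiguities affect Stage 1 directly. The first decides whether pre-dose regimen events in dosed children count towards the primary endpoint. The second decides which events permit an additional participant.

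**Working it through.** The plan gives no figure on this point, so there is none to reproduce. The check compares definitions and then gives an illustration of size.

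**1. Sources of risk against what is recorded.**

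| Source of risk (8.7) | Causality target (13.10) | Relatedness table (14.6) |
|---|---|---|
| Vector | Investigational product | Yes, as study medication |
| BiTh and ICM/IT delivery | Study procedure, administration system | Not named |
| ITI regimen | None | Not named |

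Section 14.3 uses study medication for the vector when it defines the ITT population by receipt of the full dose, so the 14.6 table is read here as vector-relatedness.

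**2. Could study procedure cover the regimen?** The term is undefined. Exclusion criterion 16 in Section 9.2 keeps the two apart: "Participants for whom any of the proposed study procedures or medications (i.e. sirolimus, trimethoprim/sulfamethoxazole) would be contraindicated". In Section 13.10, concomitant medication is something to consider and not an attribution to record. The natural reading is that the regimen has no category.

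**3. Who is left out.** Section 8.2 withdraws the child before Day 1. Section 14.3 requires partial or complete dosing with study treatment. That phrase is not defined, but Section 10.1 limits study drug to the vectors, and Section 8.2 describes the regimen as given before the AXO-AAV-GM2 treatment. The child is therefore outside the Safety Population and outside every analysis that uses it.

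**4. Size, as an illustration.** The documents give no rate of pre-Day 1 withdrawal. Assume that w children are withdrawn for regimen toxicity and that all planned children (12 in Stage 1, or 12 + 10 = 22 over both stages) are then treated without such an event. The Safety Population shows 0/n and the regimen-exposed set shows w/(n + w). Intervals are exact (Clopper-Pearson): for x events in m children, the lower limit is the 2.5% quantile of Beta(x, m − x + 1) and the upper limit is the 97.5% quantile of Beta(x + 1, m − x). With x = 0 the lower limit is 0 and the upper is 1 − 0.025^(1/m); for m = 12 this is 26.5%.

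| Treated n | w | Safety Population | Regimen-exposed set |
|---|---|---|---|
| 12 | 1 | 0/12: 0% (0 to 26.5%) | 1/13: 7.7% (0.2 to 36.0%) |
| 12 | 2 | 0/12: 0% (0 to 26.5%) | 2/14: 14.3% (1.8 to 42.8%) |
| 12 | 3 | 0/12: 0% (0 to 26.5%) | 3/15: 20.0% (4.3 to 48.1%) |
| 22 | 1 | 0/22: 0% (0 to 15.4%) | 1/23: 4.3% (0.1 to 21.9%) |
| 22 | 2 | 0/22: 0% (0 to 15.4%) | 2/24: 8.3% (1.0 to 27.0%) |
| 22 | 3 | 0/22: 0% (0 to 15.4%) | 3/25: 12.0% (2.5 to 31.2%) |

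How likely is at least one such withdrawal? For an assumed per-child risk p among 12 children starting the regimen, the chance is 1 − (1 − p)^12: 21.5% at p = 2%, 46.0% at 5% and 71.8% at 10%.

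**5. Share of regimen exposure affected.** The window before Day 1 is about 7 days. To the end of the sirolimus wean in Week 27, the share is 7/(7 + 27 × 7) = 7/196 = 3.6%. To Week 24, the end stated in Section 8.1, it is 7/(7 + 24 × 7) = 7/175 = 4.0%. The window is short, but it holds the scheduled rituximab and Solu-Medrol infusions on Day -7.

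**6. Treatment emergence and the word related.** If TEAE onset runs from gene transfer, Day -7 to Day 1 events in dosed children miss the Stage 1 primary endpoint. If it runs from the first regimen dose, they count. The documents do not choose. Section 9.4 ties its suspension triggers to the vector or the delivery procedures, while Section 8.1.1 leaves the word related unqualified. The whole four-week window in 8.1.1 lies within the regimen period.

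**The case against.** A reader might infer that regimen toxicity is lost. The documents do not support that. AEs are captured from consent, and the definition covers events related to a protocol-mandated intervention before study treatment (13.9.1.1). Causality and any resulting discontinuation are recorded for each AE (13.11). All SAEs, whatever their cause, are reported within 24 hours (13.12), and the DSMC is notified of them (17.1). The gap is in analysis. Collection does have one weak spot: Section 13.11 exempts many clinically significant laboratory changes from AE reporting, while Section 13.4 requires them.

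A reader might also infer that regimen events are bound to be misattributed. They are not: unrelated to the vector is a correct rating for a regimen-caused infection, and the investigator is told to weigh concomitant medication. What stands is that the true cause cannot then be isolated. Section 13.10 also treats any valid suspicion of the product as related, so doubtful cases lean that way.

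Nor do the documents show that the suspension rules misfire. Section 9.4 confines them to the vector or delivery procedures, and the regimen has its own stopping list in Section 8.2. The unqualified rule in Section 8.1.1 is the part left open.

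It is fair to say that a vector-exposed Safety Population suits the Stage 1 objective, which is the safety of AXO-AAV-GM2 (7.1.1). Moving its start to the first regimen dose would put vector-unexposed children into vector denominators. Stage 1 also relies mainly on listings and individual data (Sections 14 and 14.2), which softens the effect of any denominator. Finally, the eCRF is not among the documents and may already carry a regimen field.

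**Conclusion.** The point holds as a gap in attribution and in the planned analyses. The regimen has no causality category of its own, and children withdrawn for its toxicity before Day 1 are excluded by definition from all planned safety analyses. In children who are dosed, AEs still enter the overall incidence whatever their cause, subject to how TEAE is defined.

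One assumed withdrawal gives 0/12 shown against 1/13 among regimen-exposed children. It would be wrong to describe this as a denominator falling from 12 to 11, because the Synopsis and Section 8.1 plan 12 treated children, and a child never dosed is not one of them.

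The conclusion rests on reading study treatment in Section 14.3 as the vector, and on the protocol text rather than the unseen eCRF. The number of withdrawals is illustrative. If none occurs, the population gap has no effect, but the missing causality category remains.

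**What to change.** 1. Add the ITI regimen as a separate causality field in Section 13.10 and on the AE form, and include it in the Section 14.6 relatedness table.
2. Keep the vector-exposed Safety Population as the main set. Add a supplementary set of all children given at least one dose of the regimen, with its own AE table and listing.
3. Define TEAE onset, and show Day -7 to Day 1 events separately.
4. Reconcile what the word related refers to in Section 8.1.1 with Section 9.4. Which meaning applies is for the sponsor to settle.

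No dose, schedule or sample size changes. The cost is slightly more site work per AE and re-rating of AEs already recorded. That re-rating may be substantial, since first enrolment was estimated for 2020 and this protocol version is dated June 2023.
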